9.4.2 Statistical model, hypothesis, and method of analysis

There is no special hypothesis intended for this study.

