9.7 Sample size calculation

A sample size of 86 (43 for each treatment arm) can achieve 90% power to detect non-inferiority limit of 5 letter between treatment arm when significance level of the test is 0.025 and the mean (standard deviation) letter change of labeled regime arm will be around 7 (7). To eliminate the effects of incomplete data which are expected in 1 year follow-up period, a priori 20% of drop-out rate is accepted; therefore at least 104 patients (52 for each treatment arm) will be included to the study.

10 Ethical considerations**10.1 Regulatory and ethical compliance**

This clinical study was designed and shall be implemented and reported in accordance with the ICH Harmonized Tripartite Guidelines for Good Clinical Practice, with applicable local regulations (including European Directive 2001/20/EC, US Code of Federal Regulations Title 21, and Japanese Ministry of Health, Labor, and Welfare), and with the ethical principles laid down in the Declaration of Helsinki.

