3 OBJECTIVES OF THE STUDY

3.1. PRIMARY OBJECTIVE

The primary objective of this study is to demonstrate that the “wait and extend” regimen of ranibizumab is non-inferior to the posology described in the prescribing information regarding the mean change in BCVA from baseline at month 12 in Turkish patients with vision loss due to diabetic macular edema.

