5.1. SAMPLE SIZE CALCULATION

A sample size of 86 patients (43 patients in each treatment arm) will provide 90% power to determine a non-inferiority margin of 5 letters between the treatment arms with a significance level of 0.025 for the test, and the mean (standard deviation) letter change of the prescribing information regimen arm will be approximately 7 (7). A 20% discontinuation rate is initially assumed in order to account for the missing data expected for a follow-up period of 1 year; thus, at least 104 patients (52 patients in each treatment arm) will be included in the study.

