6.9 BCVA (BEST CORRECTED VISUAL ACUITY) – FROM 4 METERS WITH ETDRS

Descriptive statistics (n, mean, standard deviation, minimum, median, maximum and 95% confidence interval) for BCVA Test scores applied to both eyes will be tabulated for all 14 visits for the patient group receiving the “Approved Treatment Regimen” and until the last available visit for the patient group receiving the “Wait and Extend” treatment regimen. For both treatment groups, the change between the first and final visits will be compared using the t-test for paired sequences or Wilcoxon Signed Rank Test based on the fit of the data to normal distribution.

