6.14 EFFICACY EVALUATION

6.14.1 Visual Acuity

In order to demonstrate that the “wait and extend” regimen of ranibizumab is non-inferior to the posology described in the prescribing information, mean change in BCVA at month 12 from the baseline visit will be determined for both treatment groups, and a comparison will be made between the two groups using the Mann Whitney u test.

The number of patients with improvement in BCVA from baseline will be compared for the two treatment groups using the Chi-Square test (with Fisher’s Exact Test where appropriate).

The number of patients with improvement of 5 or more letters from baseline will be compared for the two treatment groups using the Chi-Square test (with Fisher’s Exact Test where appropriate).

The number of patients with improvement of 10 or more letters from baseline will be compared for the two treatment groups using the Chi-Square test (with Fisher's Exact Test where appropriate).

The number of patients with improvement of 15 or more letters from baseline will be compared for the two treatment groups using the Chi-Square test (with Fisher's Exact Test where appropriate).

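### The primary non-inferiority question is analysed with a Mann-Whitney test of no difference; the 5-letter margin enters no analysis, so the planned test cannot show non-inferiority

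*SAP*

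**What the plan says.** The primary objective in SAP 3.1 is to show that wait-and-extend is "non-inferior to the posology described in the prescribing information regarding the mean change in BCVA from baseline at month 12". Protocol 2.1 has the same aim.

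The margin and the significance level appear only in the sample size text. SAP 5.1 says that 43 patients per arm "will provide 90% power to determine a non-inferiority margin of 5 letters between the treatment arms with a significance level of 0.025". Protocol 9.7 and the protocol synopsis agree.

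The analysis sections do not carry this through:

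- **SAP 6.14.1** introduces the primary analysis as the one that will demonstrate non-inferiority, then says that "a comparison will be made between the two groups using the Mann Whitney u test".
- **SAP 6.9** is the only other place where BCVA change is tested: "the change between the first and final visits will be compared using the t-test for paired sequences or Wilcoxon Signed Rank Test". This is a paired comparison within each arm. The 95% confidence intervals in that section describe BCVA scores by arm and visit.
- **Protocol 9.4.2**, where the hypothesis and model belong, reads: "There is no special hypothesis intended for this study". Protocol 9.4.4 plans no supportive analysis.

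**The concern.** A non-inferiority claim needs a test or interval that rules out a deficit as large as the margin. The Mann-Whitney test, used as SAP 6.14.1 describes it, has no difference as its null hypothesis. A non-significant result leaves a 5-letter deficit possible, and a significant result against wait-and-extend does not show that the deficit reaches 5 letters. The p-value therefore does not answer the question in the title and the primary objective.

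Two consequences follow. The 90% power belongs to a margin-based test that the analysis sections do not contain. And because no decision rule is written, the result invites reading a non-significant p-value as non-inferiority. Under that reading, fewer patients or noisier measurements make success more likely.

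A smaller point concerns efficiency. The analysis makes no use of baseline BCVA, which is collected and may range from 39 to 78 letters at entry.

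**Working it through.** **Inputs.** Margin 5 letters, level 0.025, power 90%, 43 per arm, and mean (SD) change 7 (7) in the labelled arm (Protocol 9.7, SAP 5.1); 1:1 allocation (Protocol 5.3). Assumed here: a true difference of 0 for the power calculation, the same SD in both arms, and normally distributed changes. The documents do not state whether 0.025 is one- or two-sided.

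**Step 1. Reproduce the plan's sample size.** For a margin test of means,

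n per arm = 2 × (z₀.₉₇₅ + z₀.₉₀)² × SD² / margin² = 2 × (1.960 + 1.282)² × 49 / 25 = 41.2, so 42.

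The exact noncentral-t calculation gives power of 89.9% at 42 per arm and 90.6% at 43, which matches the stated 43. Reading the level as one-sided 0.05 gives 34 per arm, and reading 0.025 as two-sided gives 49. The trial was therefore sized for a one-sided 0.025 test against -5 letters.

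**Step 2. Where the two questions part.** With 43 per arm and SD 7, the standard error of the difference is 7 × √(2/43) = 1.51 letters. The half-width of the 95% CI is 1.989 × 1.51 = 3.00 letters. On the t scale:

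- non-inferiority requires an observed difference above -5 + 3.00 = -2.00 letters;
- a test of no difference is non-significant for any observed difference between -3.00 and +3.00.

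An observed difference between -3.00 and -2.00 is thus non-significant and yet fails to exclude the margin.

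**Step 3. Size of the problem if non-significant is read as non-inferior.** This rule is not in the documents; it is one possible reading of an unstated rule. Simulated normal trials (20,000 per setting), with wait-and-extend truly 5 letters worse:

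| Evaluable per arm | SD | Mann-Whitney two-sided p ≥ 0.05 | Lower 95% limit above -5 |
|---|---|---|---|
| 52 | 7 | about 6% | 2.5% |
| 43 | 7 | about 11% | 2.5% |
| 35 | 7 | about 18% | about 2.5% |
| 43 | 10 (assumed) | about 39% | about 2.5% |

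On the sizes: SAP 5.1 includes 52 per arm to allow for 20% loss, which leaves 52 × 0.8 = 41.6. SAP 5 and Protocol 4 instead randomise 86 in total; 20% loss from 43 leaves 34.4, so the 35-per-arm row is possible on that reading.

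At a true deficit of 3 letters (43 per arm, SD 7), about 26% of trials are non-significant while the 95% CI fails to exclude -5.

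**Step 4. The opposite reading.** If only a significant result in favour of wait-and-extend counts, success occurs in about 2.4% of trials when the regimens are equal, against the planned 90%.

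**Step 5. Check the remedy.** At 43 per arm and SD 7, the rule that the lower 95% limit must exceed -5 gives 90.6% power at a true difference of 0 (simulated 90.7%) and a 2.5% false-claim rate at a true -5. A Mann-Whitney test on data shifted by 5 letters gives 89.0% and 2.5%.

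**Step 6. Baseline adjustment.** If baseline BCVA and change correlate at r, residual variance falls by r². For an assumed r of 0.3 to 0.5, that is 9% to 25%.

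**The case against.** The strongest reply is that the rank test is not itself the error. Shifted by 5 letters, or paired with a Hodges-Lehmann interval compared with -5, it is a valid non-inferiority method, and SAP 6.14.1 does state its non-inferiority purpose. That is right about the method, but the SAP specifies neither device, and both address a location shift while the objective concerns a mean.

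It is also true that a significant result favouring wait-and-extend would support non-inferiority. That route is open in only about 2.4% of trials if the regimens are equal, which is the situation the sample size appears to assume.

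The error rates are conditional. No document says that a non-significant result will be read as non-inferior. The SD of 10 is not in the documents, and the picture is milder at 52 evaluable per arm. These limits stand, and the figures should be read as illustrating an unstated rule. One-sidedness is likewise an inference from the sample size, though a sound one.

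Protocol 9.4.2 may be template text, since the objective and sample size plainly concern non-inferiority. Even so, it contradicts them and leaves no hypothesis for the SAP to implement.

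Finally, an unadjusted difference in mean change is valid under randomisation, and the responder endpoints are secondary. Baseline adjustment and responder intervals are improvements; the defect does not depend on them.

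**Conclusion.** The concern holds. Followed as written, the plan gives a p-value for no difference and no means of judging it against 5 letters, so it does not test its own primary objective. The margin is in the sample size text and in no analysis.

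The absence of a margin-based analysis is read directly from the documents and rests on no assumption. The size of the damage depends on how the result would be read. If non-significant is taken as non-inferior, the false-claim rate at a true 5-letter deficit is about 11% in the planned case (43 per arm, SD 7) and ranges from about 6% to about 39% over the settings examined, against 2.5%. If only superiority counts, the chance of success with equal regimens is about 2.4% instead of 90%. These figures assume normal changes with a common SD. This must be fixed before the data are analysed.

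**What to change.** Rewrite SAP 6.14.1 and Protocol 9.4.2 to state:

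1. **Hypotheses.** With the difference defined as wait-and-extend minus labelled in mean month-12 change in study-eye BCVA, H0 is a difference of -5 letters or less and H1 is a difference greater than -5. The level is one-sided 0.025.
2. **Estimate.** The difference from a linear model with arm and baseline BCVA, with its two-sided 95% CI. An unadjusted difference is also valid; adjustment uses data already collected and can only be expected to help precision.
3. **Decision rule.** Non-inferiority is declared only if the lower limit is above -5 letters.
4. **Mann-Whitney test.** Descriptive at most, with no bearing on the primary conclusion.

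As an optional addition, report the differences in responder proportions with 95% CIs alongside the chi-square or Fisher p-values.

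The cost is protocol and SAP wording. No new data are needed, and no new patients provided 43 per arm are evaluable.

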3.1 Study design

This is a randomized controlled, multicenter, 12 month study of Lucentis (ranibizumab) that the consenting patients will participate in a screening period and will be evaluated for their eligibility to enroll the study. After the screening period and the eligibility assessment of the patient, only one eye will be selected / treated as the study eye. After eligibility confirmation at baseline, patients will be randomized into one of the treatment arms as below:

- Arm 1 - Labeled regime arm: Treatment will be given monthly and will be continued until maximum visual acuity is achieved (the patient's visual acuity is stable for three consecutive monthly assessments performed while on ranibizumab treatment). Thereafter patients should be monitored monthly for visual acuity.
- Retreatment criteria:
 - According to this protocol VA stability means BCVA \geq 84 letters (approximate Snellen equivalent of 20/20) or OCT <300 microns in the last 2 consecutive visits or no improvement can be achieved according to the investigators evaluation regarding VA and OCT measures in the last 2 visits . Stable patients do not require reinjection and should be evaluated in the next visit for reinjection.
 - If VA decreases \geq 5 letters compared to previous visit and OCT is >300 microns, patients will be retreated.
 - If VA decreases \geq 5 letters compared to the previous visit or CRT increases >50 microns compared to the previous visit, patients will be retreated.
 - After 3 monthly injections of the investigational drug laser photocoagulation can be administered if VA worsens \geq 10 letters and/or CRT increases >100 microns.
- The interval between two doses should not be shorter than 1 month.
- Arm 2 - Wait and Extend regime arm: Lucentis (ranibizumab) 0.5 mg will be injected subsequently at baseline, month 1 and 2. After the three initial loading doses, patients will be called for the control visits 1 month later. If the visual acuity has reached a stable level and there is no sign of edema on OCT, patients will not receive intravitreal injection and will be called to come back 6 weeks later. The interval is increased by 2 weeks until a maximum of 8 weeks as long as the patient presents as stable regarding visual acuity, central retinal thickness and clinical findings. If there is a negative change, the interval is shortened back to 4 weeks.

Retreatment criteria:

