- According to this protocol VA stability means BCVA \geq 84 letters (approximate Snellen equivalent of 20/20) or OCT <300 microns in the last 2 consecutive visits or no improvement can be achieved according to the investigators evaluation regarding VA and OCT measures in the last 2 visits . Stable patients do not require reinjection and should be evaluated in the next visit for reinjection.
- If VA decreases \geq 5 letters compared to previous visit and OCT is >300 microns, patients will be retreated.
- If VA decreases \geq 5 letters compared to the previous visit or CRT increases >50 microns compared to the previous visit, patients will be retreated.
- After 3 monthly injections of the investigational drug laser photocoagulation can be administered if VA worsens \geq 10 letters and/or CRT increases >100 microns.

Figure 3-1 Study design

Study Design For Labelled Regime Arm

Phase	Screening		Main Treatment			
Visit	1	2	3	4	5	6 -14
Month	0		1	2	3	4 – 12
Day	-7 to -1	B	30	60	90	120 – 360

Study Design For Wait and Extend Arm

Phase	Screening		Main Treatment			
Visit	1	2	3	4	5	Visit number may vary according to the response of the patient
Month	0		1	2	3	4 – 12
Day	-7 to -1	B	30	60	90	120 – 360

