4.1 Inclusion criteria

Patients eligible for inclusion in this study have to fulfill **all** of the following criteria:

1. Written informed consent must be obtained before any assessment is performed.
2. Male or female patients >18 years of age who have signed an informed consent
3. Patients with Type 1 or Type 2 diabetes mellitus (according to ADA or WHO guidelines) with HbA1c not more than 12.0% at screening (Visit 1). Patients should be on diet, exercise, and/or pharmacological treatment for diabetes.
4. Patients with visual impairment due to focal or diffuse macular edema with center involvement in at least one eye, as demonstrated with color fundus photography, fluorescein angiography and OCT within 28 days of the baseline treatment. If both eyes are eligible, the one with the worse visual acuity, as assessed at Visit 1, will be selected for study treatment unless, based on medical reasons, the investigator deems the other eye the more appropriate candidate for study treatment. The study eye must fulfill the following criteria at Visit 1:
 - BCVA score between 78 and 39 letters, inclusively, using ETDRS-like visual acuity testing charts at a testing distance of 4 meters (approximate Snellen equivalent of 20/32 to 20/160)
 - Decrease in vision is due to DME and not due to other causes, in the opinion of the investigator

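### The 10- and 15-letter responder comparisons should be baseline-adjusted risk differences with confidence intervals, because eyes entering at 75–78 or 70–78 letters respond only above the protocol's 84-letter stability level

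*SAP*

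**What the plan says.** Protocol 4.1 admits study eyes with a "BCVA score between 78 and 39 letters, inclusively", assessed at Visit 1.

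Protocol 3.1 gives the same stability rule for both arms. Visual acuity is stable if BCVA is at least "84 letters (approximate Snellen equivalent of 20/20) or OCT <300 microns in the last 2 consecutive visits", or if "no improvement can be achieved according to the investigators evaluation regarding VA and OCT measures in the last 2 visits". The consequence is: "Stable patients do not require reinjection and should be evaluated in the next visit for reinjection".

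SAP 6.14.1 takes four cut-offs for BCVA gain from baseline (any improvement, 5, 10 and 15 letters) and compares the arms at each by chi-square, or Fisher's exact test where appropriate. At the upper two it says "The number of patients with improvement of 10 or more letters from baseline will be compared for the two treatment groups" and "The number of patients with improvement of 15 or more letters from baseline will be compared for the two treatment groups". It plans no adjustment for baseline BCVA, no breakdown by it, and no estimate of the difference with an interval.

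Protocol 5.3 describes 1:1 allocation from a randomisation list and mentions no stratification. The responder counts are secondary objectives (Protocol 2.2, SAP 3.2) with no margin and no power statement.

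**The concern.** The entry range and the stability level are close together. An eye that starts near the top of the range has to score above 84 to make a 10- or 15-letter gain, and at 84 the protocol no longer calls for an injection at that visit. Whether such an eye responds may therefore depend heavily on where it started.

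At stake is how a secondary result can be read. If baseline BCVA strongly predicts response and the arms differ by chance in their number of high-baseline eyes, an unadjusted comparison mixes that difference with the regimen effect. With about 43 evaluable patients per arm the responder counts are small, and a chi-square p-value tells the reader neither how large the difference is nor what differences remain compatible with the data.

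**Working it through.** **The plan's own figure.** Protocol 9.7 and SAP 5.1 give 43 evaluable patients per arm for a 5-letter margin, SD 7, alpha 0.025 (taken as one-sided), 90% power and no true difference. The normal formula gives n = 2 × 7² × (1.960 + 1.282)² / 5² = 41.2, so 42 per arm. With the noncentral t distribution, 42 per arm gives 89.9% and 43 gives 90.6%. The stated figure reproduces, and 43 per arm is used below. The documents give no figure for the responder endpoints.

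**Which eyes are affected.** The Visit 1 score is taken as baseline; 39 to 78 is 40 possible scores.
- 10 letters: 74 + 10 = 84 and 75 + 10 = 85, so scores 75–78 must exceed 84. That is 4 of 40.
- 15 letters: 69 + 15 = 84 and 70 + 15 = 85, so scores 70–78 must exceed 84. That is 9 of 40. An eye at 78 needs 93.
- 5 letters: 78 + 5 = 83, so no eye is affected.

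**Share of patients.** This is an assumption, since no baseline distribution is given.
- Uniform baseline: 4/40 = 10% (10 letters) and 9/40 = 22.5% (15 letters).
- Normal, SD 10, truncated to 39–78, centred at 55 to 70: 1.7% to 16.1%, and 6.8% to 40.2%.

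**Chance imbalance.** With a share s of affected eyes, the between-arm difference in their number has standard deviation √(2 × 43 × s × (1 − s)).
- s = 0.225: √(86 × 0.225 × 0.775) = 3.9 eyes, or 9.0% of an arm.
- s = 0.10: √(86 × 0.10 × 0.90) = 2.8 eyes, or 6.5% of an arm.

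To bound the effect on the responder difference, suppose that affected eyes never respond and that the others follow a normal change with mean 7 and SD 7 (the labelled-arm values in Protocol 9.7). The others then reach 10 letters with probability 33.4% and 15 letters with probability 12.7%. A one-SD imbalance moves the difference by 6.5% × 0.334 = 2.2 percentage points (10 letters) and 9.0% × 0.127 = 1.1 points (15 letters), in either direction. If affected eyes can respond, the shift is smaller.

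**Precision of the unadjusted comparison.** In the same bounding case the arm rates are 0.90 × 33.4% = 30.1% and 0.775 × 12.7% = 9.8%. With equal rates in both arms, the 95% half-width for the difference is 1.96 × √(2 × 0.301 × 0.699 / 43) = 19 points, and 1.96 × √(2 × 0.098 × 0.902 / 43) = 13 points. A non-significant test would leave wide differences open.

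**Dilution, only if 84 acted as a hard cap.** Take true mean gains of 7 and 2 letters (SD 7), 43 per arm, a two-sided 5% test and a uniform baseline.
- 10 letters: 33.4% v 12.7% becomes 30.1% v 11.4%; power 63% becomes 57% (54% to 62% across the normal scenarios).
- 15 letters: 12.7% v 3.2% becomes 9.8% v 2.5%; power 37% becomes 29% (23% to 35%).

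If 84 is not a cap, the forced loss is zero.

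**The case against.** The strongest reply is that 84 letters is not a ceiling. It is one of three alternative conditions, and it governs whether an injection is called for at a visit, not what an eye can score. The other two can be met at any acuity, so withholding is not specific to eyes near 84. An eye can pass 84 on injections already given; in the wait-and-extend arm three doses "will be injected subsequently at baseline, month 1 and 2". If the planning change (mean 7, SD 7) applied at every baseline, an eye at 78 would have about a 50% chance of reaching 85 and about 33% of gaining 10 letters. All of this stands.

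A reader might infer more: that the eyes with the best outcome are counted as failures, and that the diluted contrast then supports non-inferiority. The documents do not support either step. An eye going from 78 to 84 has gained 6 letters. It is correctly not a 15-letter gainer, it counts at the any-improvement and 5-letter cut-offs, and its gain enters the primary mean. Non-inferiority is claimed only for mean BCVA change, with the 5-letter margin; nothing in the plan lets a non-significant responder test stand in for it. Dilution needs both an effective cap near 84 and a true difference between arms.

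It can also be said that chance imbalance is ordinary sampling variation, already reflected in the test's error rate. That is true on average over randomisations. It does not help a reader faced with one realised imbalance in a strong predictor, and it does not supply the missing estimate and interval.

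**Conclusion.** The point holds as a minor refinement. The letter ranges are exact: eyes entering at 75–78 (10 letters) or 70–78 (15 letters) respond only by exceeding 84. That their chance of responding is lower is plausible, not shown, and it is not zero. The share affected rests on an assumed baseline distribution: 10% and 22.5% if uniform, roughly 2–16% and 7–40% in the truncated-normal scenarios.

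The distortion from a typical chance imbalance is small, at most about 2 percentage points (10 letters) and 1 point (15 letters) with a uniform baseline, and has no preferred direction. The greater weakness is that a p-value alone conceals intervals of roughly ±13 to ±19 points. The tests are unpowered secondary comparisons, and the primary conclusion is untouched.

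**What to change.** In SAP 6.14.1:
- Keep the plain-gain definitions of the 10- and 15-letter responders; they match the stated objectives.
- Replace the chi-square p-value alone with the risk difference and its 95% confidence interval, adjusted for baseline BCVA. Either standardised logistic regression or Mantel-Haenszel weighting with strata below 70 and 70 or above would serve.
- As supportive output only, tabulate responders by baseline BCVA, and show the proportion with a gain of at least 10 (15) letters or a BCVA of at least 84 at Month 12. The composite should not become the main definition, because it would call a 6-letter gain from 78 a 15-letter response.

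The data are already collected, so the cost is some programming and a few lines of text. The main risk is an unstable adjusted model when 15-letter events are sparse: at 12.7%, 43 patients yield about 43 × 0.127 = 5.5 responders, so the method and a fallback should be named in advance. No change to the retreatment rule is proposed.
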